## **HAICT methodology**

HAICT treats the human-AI interaction as a signal detection problem with two observers. We generated a set of visual stimuli that both our human and “AI” observer must evaluate. This is analogous to a CADx situation where a human reader might use a CAD system to help determine if a mass is cancerous.

At the heart of the HAICT method is the use of artificial stimuli that can be precisely controlled in ways that real medical images cannot be. Thus, as shown in Figure 2, the stimuli were 20x20 square grids in which each square was a shade of red or green.

**Figure 2: Construction of HAICT stimuli**

Whether a case is “positive” or “negative” determines the numbers of red and green cells in the stimulus. For a negative trial, the number of red cells is derived from one normal distribution. For positive trials, the number is derived from another distribution with a higher mean. The difference in those means, converted to  $d'$  puts an upper limit on performance. That is, if the distributions are separated by  $d'=2.5$ , as they are in this case, even the most ‘expert’ observer cannot produce results with  $d'$  better than 2.5, except by chance. This method means that some positive cases will look negative and vice versa. It is important to explain this to participants, especially if the experiment involves feedback in order to avoid confusion and frustration.

Human and AI stimuli can be the same or they could be generated separately so that the maximum performance of the two observers can be independently varied. In this experiment, both the AI and human have a maximum performance of a  $d'$  of 2.5.

### **Specific Method**

We tested 13 naïve observers (avg age 31, 8 female, 5 male). All had normal color vision as assessed by Ishihara color plates and acuity of 20/25 or better.

Two conditions were be tested:

1. Baseline - No AI input. Observer classifies each case as "bad" or "not" bad on their own.
2. Second Reader - The observer makes an initial decision about every case. The simulated AI silently classifies stimuli using a "conservative criterion" ( $c = 0.5$ ). The logic for the conservative criterion is that the second reader is being used to cut down on false positive responses and so it is intended to raise questions about positive human responses that might be marginal. If the observer and AI disagree, then the AI informs the human observer. The observer is then given a chance to either change their response or go with their first opinion.

In each of these conditions, the prevalence of "positive cases" is varied in separate blocks. The percentage of targets could be 10%, 33%, 67% or 90%. Humans are known to become more conservative at low prevalence, missing more targets (Horowitz, 2017). Thus, there were 8 blocks per Observer (2 conditions X 4 levels of prevalence). Each Observer ran 200 trials in each block. Block order was randomized.

Stimuli were present in a darkened room on Macintosh desktop computers with Os at an approximate 60 cm viewing distance.

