Background: In a variety of visual search experiments, both basic and clinical, the data have been consistent with a situation where the variability of the signal (or target) is greater than the variability of the noise (distractors). As an example, in screening for breast cancer, this would mean that the variability of backgrounds in mammograms would be less than the variability in actual signs of cancer (the signal in these “signal detection theory” (SDT) terms. The classic sign of this greater signal variability is a “zROC” function with a slope < 1 – typically around 0.6. A slope of 1.0 is indicative of an equal variance 2AFC task; that is, the same amount of variability in the signal and the noise. The present experiment is part of a series where we systematically vary the parameters of a simple 2-alternative forced-choice (2AFC) task where participants decide if a stimulus is “good” or “bad”. Participants can also be helped by a simulated AI system. This is our **Human-AI Collaboration Tester (HAICT)**.

For the HAICT task that we have been testing in this series of experiments, we would expect equal variance, but we think it would be worth checking so we will systematically vary prevalence which will shift criterion. That will sweep out an ROC curve that we can examine.

We will also test the Second Reader faux-AI in order to determine if low prevalence makes Second Reader worse.

- (H1): We expect to replicate the finding that human criteria become more conservative as prevalence declines.
- (H2): We predict that the slope of the resulting zROC will be 1.0.
- (H3): We hypothesize that low prevalence will make Second Reader AI less effective because the positive predictive value of its comments will be low.

1. **Dependent variable.** Describe the key dependent variable(s) specifying how they will be measured.

The main dependent variables of interest are accuracy (and the signal detection derivatives of accuracy, d' and c), reaction time, and subjective ratings on the survey following each block.

2. **Conditions.** How many and which conditions will participants be assigned to?

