This series of experiments investigates how changing the input from a simulated AI can affect the decisions made by human observers in a two-alternative forced choice task (like the decision to recall a woman for further examination in mammography). We have developed a paradigm called the Human-AI Collaboration Tester (HAICT) that allows for efficient testing of interactions between a human and a simulated AI.

The observers' task in all conditions is to give a 2AFC decision about whether a stimulus is "bad" or "not bad." To use language roughly mimicking a medical diagnosis, each stimulus is referred to as a "case." Observers are asked to make a 2AFC decision about arrays of colored shapes. The decision is made based on the predominant color of the case. The number of elements of each color are drawn from one of two normal distributions, one for positive (bad) stimuli and the other for negative (not bad) stimuli.

The results from previous HAICT experiments (3 and 4) showed that human performance in the Second Reader condition drops off significantly at low prevalence. Performance in the Second Reader condition was better than Baseline when the prevalence of bad cases was 50% but was significantly worse than Baseline when prevalence was only 10%. In this experiment, we manipulate the prevalence of "bad" cases in the Second Reader and Baseline conditions. Four different prevalence rates will be tested – 10%, 33%, 67%, and 90%. Observers will complete 8 blocks (2 AI rules x 4 prevalence rates), and block order is random.

AI rules to be tested:

1. Baseline - No AI input. Observer classifies each case as "bad" or "not" bad on their own.
2. Second Reader - The observer makes an initial decision about every case. The AI silently classifies stimuli using a conservative criterion ($c = 0.5$). The logic for the conservative criterion is that the second reader is being used to cut down on false positive responses and so it is intended to question positive human responses that

might be marginal. If the observer and AI disagree, then the AI informs the human observer. The observer is then given a chance to either change their response or go with their first opinion.

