As in Experiments 1-5, the AI d-prime is fixed at 2.2. Feedback is known to increase the prevalence effect, so feedback will be given in both the practice and the test trials. Observers will complete 20 practice trials and 200 test trials in each block. Immediately after each block is completed, observers will be shown a summary of their performance. After the Second Reader blocks, they will also be asked to answer three subjective questions about the usefulness of the AI (see "Files" for more details).

3. Analyses. Specify exactly which analyses you will conduct to examine the main question/hypothesis.

First, we summarize the number of hits, true negatives, misses, and false alarms in each block. From this, we can calculate the accuracy, the positive predictive value, sensitivity (d-prime), and the criterion for each observer under each of the different conditions. Given measures of performance at 4 levels of prevalence, we can estimate the ROC curve ($pHit \times pFA$) and the zROC function ($zHit \times zFA$). We will test the hypothesis that the slope of the zROC is equal to 1 (the consequence of an equal variance 2AFC task).

4. More analyses. Any secondary analyses?

We will look to see if the observers' subjective opinions about the AI are correlated with variables such as the empirical d-prime, or the positive predictive value.

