## Data analysis

One observer was removed for poor performance. For the remaining 12 Os, we performed standard signal detection analysis. For each condition, we computed the probability of a “hit” or true positive response (correct positive responses / total positive trials) and “false alarms” or false positive response (false positive responses / total negative trials). These values are converted to “z-scores” (=inverse of the standard normal cumulative distribution), zHit & zFA. From those values,  $d'$  = zHit-zFA and criterion, ‘c’, = (zHit-zFA)/-2. Response time can also be looked at but is not of particular interest in this experiment.

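### No analysis uses block position, so any practice or fatigue trend in d' stays as noise, not bias, in the Second Reader versus Baseline comparison (H3)

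*Combined protocol and SAP*

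**What the plan says.** The Protocol, item 2 (Conditions), states: "Observers will complete 8 blocks (2 AI rules x 4 prevalence rates), and block order is random". The Combined protocol and SAP, Specific Method, confirms this with "Block order was randomized" and describes the observers as naive. Neither document mentions a Latin square or other balancing of positions.

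On exposure, the Protocol says "Observers will complete 20 practice trials and 200 test trials in each block" and "feedback will be given in both the practice and the test trials".

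On the sample, the Combined protocol and SAP, Data analysis, says: "One observer was removed for poor performance. For the remaining 12 Os, we performed standard signal detection analysis".

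The hypothesis at issue is H3: "We hypothesize that low prevalence will make Second Reader AI less effective because the positive predictive value of its comments will be low". The planned analyses (Protocol items 3 and 4; Combined protocol and SAP, Data analysis) cover hit and false-alarm rates, accuracy, positive predictive value, d', c, the ROC and zROC, a test that the zROC slope is 1, and correlations with the subjective ratings. The slope test is the only hypothesis test named. Block position, period, learning and carry-over appear nowhere.

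**The concern.** In effect this is an eight-period crossover. Untrained observers receive feedback over 8 x 200 = 1,600 test trials, so learning or fatigue is plausible. Random order stops a trend from favouring either AI rule on average. In a sample of 12, however, the Second Reader and Baseline blocks at a given prevalence will usually sit at somewhat different mean positions. If d' moves with position, that chance imbalance enters the estimated difference, and summaries by condition cannot separate it out.

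What is at stake is precision for H3 in a small study. The 10% and 90% blocks each have only 20 trials in the rarer class, so d' there is already imprecise.

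**Working it through.** The plan states no practice effect, SD, power or effect size, so there is no figure of its own to reproduce.

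**Inputs from the documents.** 8 blocks; 200 test trials per block; 20, 66, 134 or 180 positive cases per block at the four prevalences; 13 - 1 = 12 observers.

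**Assumptions, not in the documents.** True d' of 2.0; criterion at 75% of the optimal shift for each prevalence; a linear trend of total size G in d' from block 1 to block 8; observer-by-block SD of 0 or 0.2.

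**Step 1: chance spread of positions.** A single position from 1 to 8 has variance 63/12 = 5.25. Two blocks of one observer cannot share a position, so their difference has variance 2 x 5.25 x 8/7 = 12. Averaged over 12 observers the variance is 12/12 = 1. The mean position difference therefore has an SD of one full block.

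**Step 2: variance from the trend.** Each position is worth G/7, so the trend adds (G/7)^2 x 12 to one observer's two-block difference. At G = 0.3 this is 0.0220; at G = 0.5 it is 0.0612.

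**Step 3: sampling variance of d'.** Per block it is H(1-H)/[n_pos x phi(zH)^2] + F(1-F)/[n_neg x phi(zF)^2], where H and F are the hit and false-alarm rates. Doubled for a difference of two blocks, this gives 0.223 at 10% or 90% prevalence and 0.101 at 33% or 67%. An observer-by-block SD of 0.2 adds 2 x 0.04 = 0.08, giving 0.303 and 0.181.

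**Step 4: inflation of the standard error.** This is sqrt(1 + Step 2 / Step 3) - 1. For example, at G = 0.5 and 10% prevalence: sqrt(1 + 0.0612/0.223) - 1 = 12.9%.

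| Total gain G | 10%/90%, SD 0 | 33%/67%, SD 0 | 10%/90%, SD 0.2 | 33%/67%, SD 0.2 |
|---|---|---|---|---|
| 0 | 0% | 0% | 0% | 0% |
| 0.1 | 0.5% | 1.2% | 0.4% | 0.7% |
| 0.2 | 2.2% | 4.7% | 1.6% | 2.7% |
| 0.3 | 4.8% | 10.4% | 3.6% | 5.9% |
| 0.5 | 12.9% | 26.7% | 9.6% | 15.7% |

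The interaction contrast of 10% against 90% has the same percentages as the 10%/90% columns, because its sampling and trend variances both double.

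**Step 5: what adjustment recovers.** A simulation used 800 runs per setting, 12 observers by 8 blocks, observer and cell effects, and assumed criteria of +0.5, +0.15, -0.15 and -0.5. For the 10% prevalence difference with observer-by-block SD 0 and a linear trend, adding linear position moved the standard error as follows:

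- G = 0: 0.127 to 0.128 (about 1% worse)
- G = 0.2: 0.138 to 0.137
- G = 0.4: 0.151 to 0.139 (8% better)

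With a learning curve that saturates early, the gain at G = 0.4 was about 4-6%. The mean estimate stayed near zero with or without adjustment, which confirms that the issue is precision and not bias.

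**The case against.** The strongest reply is that the whole effect rests on a practice gain the documents never give, and that below about 0.2 in d' the point all but disappears. That stands, and it is why the range here starts at zero. Two features of the plan may also limit practice: the 20 practice trials before each block, and the stimulus ceiling of d' 2.5 (Combined protocol and SAP, HAICT methodology). The ceiling does not exclude a gain of 0.3 to 0.5 from a start near 2.0.

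A second reply is that no model for H3 exists to which a term could be added. This also stands. The missing H3 test is the larger gap, and the position term belongs in that test once it is written.

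Three stronger readings are tempting, and the documents do not support them:

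- **That order biases H3.** Randomisation prevents this on average. An unadjusted within-observer comparison remains valid, only less precise.
- **That H1 suffers in the same way.** H1 reads "We expect to replicate the finding that human criteria become more conservative as prevalence declines". The usual criterion is -(zHit + zFA)/2. A symmetric gain raises zHit and lowers zFA equally, which leaves it unchanged. H1 loses precision only if the criterion itself drifts, and nothing in the documents shows that. The criterion formula printed under Data analysis equals -d'/2 and would carry practice into c, but that formula is a separate error.
- **That the loss is as large as 61%.** That figure is variance, not standard error. It needs a gain of 0.5, the 33% or 67% blocks and no observer-by-block variation, all at once.

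**Conclusion.** The point holds as a minor loss of precision for H3. Twelve naive observers complete eight randomly ordered blocks with feedback, and no analysis uses position. For an assumed total linear d' gain of 0 to 0.5, the unadjusted standard error of the Second Reader minus Baseline d' difference is inflated by 0-13% at 10%/90% prevalence and by 0-27% at 33%/67%. With an observer-by-block SD of 0.2 the upper ends fall to about 10% and 16%. A saturating curve reduces what a linear term can recover.

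The loss is smallest at the extreme prevalences, including the low prevalence that H3 is about, because sampling error dominates there. The size is uncertain because every input beyond the block, trial and observer counts is assumed. The omission does not invalidate any planned result.

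**What to change.** Specify the H3 test as a within-observer model for d' with AI rule, prevalence and their interaction, a random observer effect, and block position (1 to 8, linear). Report the unadjusted result beside it. Apply the same term to c only as a check for criterion drift.

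The cost is one parameter, about 1% in standard error if there is no trend. Two conditions apply. The documents do not say that block position is stored, so it must be recoverable from the data files. The Combined protocol and SAP describes testing and analysis in the past tense, so if the term is added after data collection it must be labelled as such.

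The term does not remove carry-over from the prevalence of the preceding block. Label: cheap improvement.

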## Data analysis

One observer was removed for poor performance. For the remaining 12 Os, we performed standard signal detection analysis. For each condition, we computed the probability of a “hit” or true positive response (correct positive responses / total positive trials) and “false alarms” or false positive response (false positive responses / total negative trials). These values are converted to “z-scores” (=inverse of the standard normal cumulative distribution), zHit & zFA. From those values,  $d'$  = zHit-zFA and criterion, ‘c’, = (zHit-zFA)/-2. Response time can also be looked at but is not of particular interest in this experiment.

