**Figure 1: Two-alternative forced-choice decisions as signal detection problems.**

In their simplest form, decision errors can arise when the observer is faced with a two-alternative forced-choice decision (e.g. Is this cancer or not?). In the terms of signal detection theory, as cartooned in Figure 1, truly negative and positive cases can be thought to produce overlapping distributions of internal response values within the observer. To make a decision, the observer must establish some ‘criterion’, ‘c’; declaring all values above criterion to be positive and those below to be negative. The separation between the positive and negative distributions determines the difficulty of the decision and can be quantified by the parameter,  $D'$  (though the situation is

more complex and other metrics are more useful if, for example, the variance of the two distributions is not the same). When the distributions overlap, the observer *must* make errors: False positive (FP) or False alarm errors, shaded red, and False Negative (FN) or miss errors, shaded green. Shifting criterion can change the mix of errors but cannot eliminate them. A manipulation that increases  $D'$  reduces errors.

Two observers will typically perform better than either alone, especially if the ‘noise’ that degrades their performance is not identical. The relationship of two observers in SDT terms has been formalized by Sebastian and Geisler (2018). A CAD AI that offers its own assessment of the stimulus can be thought of as a second observer. The focus of our interest is in the interaction of that second observer with a human who is making the ultimate decision.

Search and recognition errors can arise when the perceptual task involves spatial uncertainty. If the task involves a search for possible targets (e.g. signs of breast cancer), it is possible to fail because you never looked at the target (search errors) or because, when you looked at the target, its importance was not registered (recognition errors). The use of AI to reduce these errors is important but not considered in this experiment.

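### d' is the only discrimination index defined, yet it is free of criterion only at zROC slope 1; the slope test has no stated consequence for H3

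*Combined protocol and SAP*

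**What the plan says.** Combined document, Data analysis: for the 12 observers kept, "we performed standard signal detection analysis". For each condition, hit and false-alarm rates become z-scores, and d' is given as "zHit-zFA and criterion, ‘c’, = (zHit-zFA)/-2". No other discrimination index is defined, and the section does not mention the zROC slope.

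Protocol, item 3 (Analyses): accuracy, positive predictive value, d' and "the criterion for each observer under each of the different conditions" are calculated. The zROC is estimated from the four prevalence levels and the hypothesis that its slope is 1 is tested.

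Protocol, Background: visual search data often give a zROC "with a slope < 1 – typically around 0.6". For this task the authors expect equal variance, and H2 reads "We predict that the slope of the resulting zROC will be 1.0". H3 says that Second Reader becomes less effective at low prevalence; no test or outcome is named for it.

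Combined document, text to Figure 1: after introducing d', the authors concede that "other metrics are more useful if, for example, the variance of the two distributions is not the same".

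**The concern.** The plan states an assumption and tests it, but attaches no consequence to the result. zHit − zFA is a criterion-free measure of discrimination only when the zROC slope is 1. The design moves criterion on purpose: prevalence runs from 10% to 90%, and H1 predicts that criterion follows. At a slope below 1, d' rises as observers become more conservative even if they discriminate no better.

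At stake is the reading of H3. If the effectiveness of Second Reader is judged on d', part of any difference across prevalence may be movement along a single ROC. The slope may also differ between Baseline and Second Reader, and the documents do not address that case.

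**Working it through.** The documents give no H3 effect size, sample-size calculation or alpha, so there is no planned figure to reproduce.

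**Inputs from the documents.** Prevalence 10, 33, 67 and 90%; 200 trials per block, hence 20 positives at 10% and 20 negatives at 90%; 12 analysed observers; AI criterion 0.5 at every prevalence; AI d' 2.2 (Protocol, item 2) and maximum d' 2.5 (combined document, text to Figure 2); slope 1 predicted, about 0.6 called typical of visual search.

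**Assumptions.** Binormal zROC; true d_a 2.0 to 2.5; criterion c = λ·ln((1−p)/p)/d_a, with λ = 0.5 (half the ideal shift) or 1 (ideal shift); slopes 0.6 and 0.8. I use the standard c = −(zHit + zFA)/2.

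**Step 1: algebra.** Let zHit = a + s·zFA, with a = d_a·√((1+s²)/2). Then d' = a − (1−s)·zFA, so a criterion shift changes d' by (s−1)·ΔzFA. Per unit of c, the change is 2(1−s)/(1+s): 0.50 at s = 0.6, 0.22 at s = 0.8, 0 at s = 1.

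Example: s = 0.6 and d_a = 2.0 give a = 2.0 × √0.68 = 1.65. At zFA = −0.5, d' = 1.65 + 0.4 × 0.5 = 1.85. At zFA = −2.0, d' = 1.65 + 0.4 × 2.0 = 2.45.

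**Step 2: drift across the design, one fixed ROC.** With d_a = 2.2 and s = 0.6:

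| Criterion shift | 10% | 33% | 67% | 90% |
|---|---|---|---|---|
| Half ideal, d' | 2.52 | 2.35 | 2.19 | 2.02 |
| Ideal, d' | 2.77 | 2.43 | 2.11 | 1.77 |
| Either, d_a | 2.20 | 2.20 | 2.20 | 2.20 |

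Over d_a 2.0 to 2.5 and both shifts, d' at 10% minus d' at 90% is 0.44 to 1.10 at s = 0.6, 0.19 to 0.49 at s = 0.8, and 0 at s = 1. For scale, the binomial-only standard error of a 12-observer mean d' at 10% prevalence is about 0.10, or 0.14 for a difference of two such means (assumed d' 2.2, c 0.44).

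**Step 3: Second Reader minus Baseline.** With a common slope, the artefact at prevalence p is (s−1)·δ(p), where δ(p) is the Second Reader minus Baseline difference in zFA due to criterion. Between 10% and 90% it is (s−1)·[δ(10%) − δ(90%)], which is exactly 0 if δ is constant. At a single prevalence, a criterion difference of 0.2 to 0.4 in c (assumed) gives 0.10 to 0.20 at s = 0.6 and 0.04 to 0.09 at s = 0.8.

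**Step 4: slope 1 in Baseline, but not in Second Reader.** Suppose an equal-variance human (d' 2.0 or 2.2) optimally combines advice from a conditionally independent AI (d' 2.2 or 2.5, c = 0.5). Baseline slope is 1. The fitted Second Reader slope is 0.80 to 0.89. Second Reader d' is higher at 10% than at 90% by 0.10 to 0.17 under half shifts and by 0.19 to 0.30 under ideal shifts (largest case 2.917 − 2.613 = 0.304). Baseline d' does not drift, so all of this enters the contrast. In that largest case the slope is 0.815, and d_a with that slope is 2.75 at both 10% and 90%. Over all the cases d_a varies by at most about 0.03 across the four prevalences; this zROC is not exactly straight.

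**The case against.** The strongest reply is that the authors did not overlook the assumption. The 0.6 slope describes visual search in general; for this task they expect equal variance, describe two normal distributions separated by a single d', and test the slope. That stands: the risk is conditional, and the gap is the missing fallback.

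Several stronger readings are tempting, but the documents do not support them:

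- **That H3 is to be analysed with d'.** No outcome is named for H3; accuracy and positive predictive value are also computed, and the hypothesis itself refers to predictive value. But both depend on prevalence and criterion, so neither replaces a discrimination index.
- **That the drift necessarily enters the H3 contrast.** Step 3 shows that it cancels with equal slopes and a constant shift.
- **That Second Reader must make observers more conservative still.** The AI flags disagreements in both directions. For an observer with assumed d' 2.2 making half to all of the ideal shift, c at 10% prevalence is about 0.5 to 1.0, so an AI at 0.5 is no more conservative than that observer. Useful advice also lowers zFA by moving the ROC, and that gain is not spurious.
- **That the artefact could mimic H3.** Within Second Reader that needs a slope above 1, and the documents give no reason to expect one.
- **That H1 is undermined.** On a fixed ROC, standard c is monotone in zFA for any positive slope, so the direction of H1 survives.

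**Conclusion.** The point holds as a missing fallback. d' is computed in every condition and is the only discrimination index defined, while the slope test that would justify it leads nowhere. Four zROC points per observer, with 20 positives or 20 negatives in the extreme blocks, cannot establish slope 1 by non-rejection, and a Baseline slope of 1 would not vouch for Second Reader.

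The size depends on assumed slopes and criterion shifts: several tenths of a d' unit across prevalence for slopes of 0.6 to 0.8, and 0.10 to 0.30 within Second Reader in the model with an equal-variance human. The bias affects a d' comparison across prevalence within Second Reader, and a Second Reader minus Baseline contrast when slopes differ between conditions or the criterion shift differs by prevalence. With slope below 1 it favours low prevalence, so the danger is a masked H3. If both slopes are 1 there is no artefact.

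**What to change.** 1. Estimate the zROC slope with a 95% CI separately for Baseline and Second Reader, pooled across observers or by a hierarchical fit, because the extreme blocks are sparse. A Baseline slope alone would miss the situation in step 4.
2. For H3, report d_a = √(2/(1+s²))·(zHit − s·zFA) and the matching criterion c_a beside d' and c, using each condition's own slope. Report c_a for H1 as well.
3. State that the H3 discrimination conclusion rests on d_a if either condition's slope CI excludes 1.
4. Compute c, and hence c_a, from zHit + zFA. As printed, c equals −d'/2 and cannot measure criterion; that is a separate correction.

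The cost is two formulas and one slope fit per condition on data already collected, with no new observers. The downside is that d_a carries the sampling error of the slope, so its intervals should include it. This is a cheap improvement.

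### The only formula given for the criterion c is -d'/2, so as printed it does not measure criterion and cannot test H1

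*Combined protocol and SAP*

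**What the plan says.** The Data analysis section of the Combined protocol and SAP converts the hit and false-alarm rates to z-scores with the inverse normal distribution. It sets d' equal to zHit minus zFA and gives the criterion as "criterion, ‘c’, = (zHit-zFA)/-2". This is the only formula for c in either document. Item 3 (Analyses) of the Protocol says that the criterion will be calculated for each observer and condition, but does not say how.

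Other parts of the documents bear on what c should be:

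- **H1 (Protocol, Background):** "We expect to replicate the finding that human criteria become more conservative as prevalence declines".
- **Outcomes (Protocol, item 1):** "The main dependent variables of interest are accuracy (and the signal detection derivatives of accuracy, d' and c), reaction time". Here d' and c are two separate measures.
- **The AI (Protocol, item 2, Second Reader):** "The AI silently classifies stimuli using a conservative criterion", with c given as 0.5. Specific Method in the Combined protocol and SAP gives the same value.
- **Meaning of criterion (Combined protocol and SAP, text with Figure 1):** "Shifting criterion can change the mix of errors but cannot eliminate them". The separation of the two distributions is described there as the separate quantity D'.

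**The concern.** The same difference, zHit minus zFA, appears in both definitions, so the printed c carries no information beyond d'. Yet c is a main outcome, and H1 is a statement about how it moves with prevalence. If the printed formula was applied, three things follow:

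1. Under equal variance, which the study predicts, prevalence moves the criterion and leaves d' alone. Printed c would then stay flat however far the criterion moved.
2. If the zROC slope is below 1, printed c would move in the direction opposite to H1.
3. Any change in d' would be reported as a change in criterion. Item 2 of the Protocol says that in previous experiments "human performance in the Second Reader condition drops off significantly at low prevalence". If a drop of that kind were in d', printed c would rise at low prevalence and look like the conservative shift H1 predicts, with no criterion change behind it.

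**Working it through.** **Inputs.** The formulas for d' and c come from Data analysis. The AI criterion of 0.5 comes from Protocol item 2 and Specific Method. The AI d' is 2.2 in the Protocol (end of item 2) and 2.5 in the Combined protocol and SAP (text with Figure 2). That difference is a separate matter, so both values are used. The zROC slopes of 0.6 (described as typical) and 1.0 (H2) come from the Protocol Background. Values marked as assumed are not in the documents.

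**Step 1: the identity.** c(printed) = (zHit - zFA)/(-2) = -(zHit - zFA)/2 = -d'/2. No data or model is needed.

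**Step 2: the stated AI criterion.** Under equal variance, with the cut-off measured from the midpoint of the two distributions, zHit = d'/2 - c and zFA = -d'/2 - c. With c = 0.5:

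| AI d' | zHit | zFA | Printed: (zHit - zFA)/-2 | Plus sign: (zHit + zFA)/-2 |
|---|---|---|---|---|
| 2.2 | 0.60 | -1.60 | -1.10 | 0.50 |
| 2.5 | 0.75 | -1.75 | -1.25 | 0.50 |

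The last column returns 0.50 by construction, so it does not prove what was intended. The fourth column is the informative one: printed c cannot be positive when d' > 0, so no setting of such an AI could give 0.5. The midpoint convention also fits the text. Measured from the negative mean instead, 0.5 would lie below the midpoint (1.10 or 1.25), which would be a liberal cut-off, not the conservative one the documents describe.

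**Step 3: prevalence shifts the criterion and d' is constant.** Assume, for illustration, c = ln((1-p)/p)/d' with d' = 2.2.

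| Prevalence | c, plus-sign form | c, printed |
|---|---|---|
| 10% | +0.999 | -1.100 |
| 33% | +0.322 | -1.100 |
| 67% | -0.322 | -1.100 |
| 90% | -0.999 | -1.100 |

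The plus-sign form shows the pattern of H1. The printed form shows nothing.

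**Step 4: zROC slope other than 1.** Let zHit = a + s·zFA, and let zFA change by D. The plus-sign c changes by -(1+s)D/2 and printed c by (1-s)D/2. The ratio is -(1-s)/(1+s):

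- s = 1.0: 0
- s = 0.8: -0.2/1.8 = -0.11
- s = 0.6: -0.4/1.6 = -0.25

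Example with s = 0.6, assuming a = 1.32 and zFA running from -2.10 (strict) to -0.10 (lax):

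- At zFA = -2.10, zHit = 0.06. Plus-sign c = +1.02 and printed c = -1.08.
- At zFA = -0.10, zHit = 1.26. Plus-sign c = -0.58 and printed c = -0.68.

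Going from lax to strict, the plus-sign c rises by 1.60 and printed c falls by 0.40.

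**Step 5: d' changes and the criterion is fixed.** The change in printed c is minus half the change in d'. Observer d' is not given, so these values are assumed:

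- d' from 2.0 to 1.8: printed c goes from -1.00 to -0.90, a rise of 0.10.
- d' from 2.0 to 1.5: printed c goes from -1.00 to -0.75, a rise of 0.25.

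Both would read as a more conservative observer.

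**The case against.** The strongest reply is that this is a slip of one character and the intent is plain. The section calls its analysis standard, the documents treat d' and criterion as distinct throughout, and a positive c is used for the AI. The text was also read from PDF by a program, so a plus sign misread as a minus cannot be ruled out. No result computed from the printed form is shown. The hit and false-alarm rates are calculated for each condition, so a shift of the operating points with prevalence could be seen without c. The only hypothesis test the Protocol spells out is the zROC slope (H2), which does not use c.

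Much of this stands. A misprint is the likeliest explanation, the code may be correct, and H1 can be recovered from data already collected.

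The illustrations also have limits. The slope example departs from H2, and with unequal variances the plus-sign c is itself an imperfect index of the cut-off. The d' example needs the Second Reader drop to have been in d', where the Protocol says only that performance fell. At low prevalence the two effects push printed c in opposite directions, so no net bias can be stated.

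None of this rescues the formula. It is the only working definition of a main outcome, and a reader who follows it reports d' twice and never measures criterion.

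**Conclusion.** The formula is wrong as written. That printed c equals -d'/2 follows from the sentence alone and rests on no assumption. It conflicts with the AI's stated c of 0.5, where it gives -1.10 or -1.25, and with the treatment of d' and criterion as separate quantities.

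The effect on H1 is conditional on the printed form having been run, which the documents do not settle. If it was, the share of a criterion shift that printed c would show is 0 at slope 1.0 and -0.25 at slope 0.6. A fall in d' of 0.2 to 0.5 (assumed) would appear as a conservative shift of 0.10 to 0.25. H1 could then not be validly tested on c. The hit and false-alarm rates, d', accuracy, positive predictive value and the H2 slope test do not depend on c and are sound on this point.

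**What to change.** In Data analysis, replace the criterion formula with c = -(zHit + zFA)/2 and keep d' = zHit - zFA. Check the source file to exclude a PDF reading error. Check the analysis code, and state in the document which form it used. If the code used the printed form, recompute c for every observer and block and repeat any analysis of H1. If it used the plus-sign form, nothing needs to be re-run.

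The cost is one sign in the text and a short code check, plus at most one re-run of the criterion calculation. No new data are needed.
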